5.1.1.2.2 Hypersensitivity Reactions and Anaphylaxis/ Hypersensitivity-Like Reactions

Hypersensitivity reactions and anaphylaxis have been described with SC administration of monoclonal antibodies (Corominas et al. 2014). Signs and symptoms may include acute onset (minutes to several hours) of one or more of the following: respiratory compromise, reduced blood pressure, skin-mucosal involvement, or GI symptoms (Sampson et al. 2006). The potential for hypersensitivity to MSTT1041A in humans is unknown. However, as with any large-molecule therapeutic, administration of MSTT1041A may result in systemic reactions. Systemic reactions to large-molecule therapeutics can be IgE or non-IgE mediated or due to the release of cytokines and are generally characterized by signs and symptoms such as skin rash, urticaria, pruritus, local or diffuse erythema, angioedema, fever, chills, cough, dyspnea, wheezing, bronchospasm, nausea, vomiting, diaphoresis, chest pain, tachycardia or bradycardia, and/or hypotension, which can be severe or life threatening. Effects typically occur during or within several hours after drug administration, but they may be delayed.

Refer to the MSTT1041A Investigator's Brochure for details about reports of adverse events of hypersensitivity reactions and anaphylaxis/hypersensitivity-like reactions.

5.1.1.2.3 Infection

The intended mechanism of action of MSTT1041A suggests inhibitory effects on immune responses mediated by Th2 cells, leading to the possibility of a decrease in the

MSTT1041A/UTTR1147A—Genentech, Inc.
59/Protocol GA42469, Version 4

protective response to infection, particularly helminthic infections (Molofsky et al. 2015). However, as described in Section 5.3 of the MSTT1041A Investigator's Brochure, a lack of significant differences in levels of exploratory biomarkers fractional exhaled nitric oxide (reflecting airway IL-4/IL-13 activity) and serum IL-5 between MSTT1041A-treated and placebo patients in Study GB39242 (patients with asthma) may reflect a limited effect on Type 2 inflammation. Refer to the MSTT1041A Investigator's Brochure for details about infections related to study treatment.

5.1.1.2.4 Exacerbation of Cardiovascular Disease

Published studies involving mouse models of cardiovascular disease or in vitro culture systems describe potential cardioprotective and atheroprotective roles of the IL-33/ST2 axis (Sanada et al. 2007; Miller et al. 2008; Seki et al. 2009; McLaren et al. 2010; Wasserman et al. 2012). For example, after experimentally induced acute left ventricular pressure overload, which could be relevant to clinical scenarios involving increased afterload (e.g., left-sided congestive heart failure or acute hypertension), ST2^{-/-} mice had more left ventricular hypertrophy, more fibrosis, and impaired survival relative to their wild-type littermates (Sanada et al. 2007). However, the translatability of these findings remains uncertain. In addition, studies with conflicting data exist (Demyanets et al. 2011; Abston et al. 2012; Martin et al. 2015).

Evidence has shown that the sST2 receptor is a prognostic biomarker of cardiovascular disease outcome (Sabatine et al. 2008; Shah et al. 2009; Weir et al. 2010). Although published findings suggest a possible risk of exacerbation of existing cardiovascular disease in humans, there are no identified cardiovascular risks associated with inhibiting the IL-33/ST2 axis in humans.

Refer to the MSTT1041A Investigator's Brochure for details about the preclinical and clinical experience associated with the potential risk of cardiovascular disease.

5.1.2 Risks Associated with UTTR1147A (IL-22Fc)

5.1.2.1 Identified Risks

5.1.2.1.1 Dermatologic Reactions

In nonclinical and clinical studies, UTTR1147A caused on-target dose-dependent reversible skin changes, including pruritus, dry lips and skin, patchy erythema, skin exfoliation (primarily on the face and upper body), and skin discomfort. In the Phase I SAD study GA29468 in healthy volunteers, the MTD of 90 µg/kg IV was determined on the basis of the intensity of erythema, pruritus, and skin hyperesthesia reported by 3 of 4 subjects who received UTTR1147A at 120 µg/kg IV. Most dermatologic manifestations at doses of up to 90 µg/kg were mild (Grade 1) or moderate (Grade 2). Dermatologic findings appeared within a week of dosing, were manageable with topical emollients, and resolved within approximately 2 weeks of onset.

In the Phase Ib MAD in healthy volunteers and patients with IBD (Study GA29469), similar dermatologic findings have been observed at all dose levels tested (30 µg/kg IV).

MSTT1041A/UTTR1147A—Genentech, Inc.
60/Protocol GA42469, Version 4

Q2W, 60 µg/kg IV Q2W, 60 µg/kg IV Q4W, and 90 µg/kg IV Q2W) after the first or second dose of UTTR1147A. In healthy volunteers, two doses of UTTR1147A at 90 µg/kg IV Q2W caused severe (Grade 3) skin discomfort, hyperesthesia, and erythema with minimal relief from topical emollients or topical corticosteroids but were self-limited and resolved after discontinuation of UTTR1147A treatment, yielding and MTD of 60 µg/kg IV Q2W.

In UC patients, two doses of UTTR1147A at 90 µg/kg IV q2wk caused moderate (Grade 2) erythema that were managed with topical emollients and resolved within 4–10 weeks after onset but UTTR1147A was better tolerated and no MTD was reached. Overall, dermatologic events (e.g., dry skin, erythema, skin exfoliation, and skin discomfort) appeared within the first month of dosing, were manageable with topical emollients, and reversible within 4 weeks to 3 months after onset. The drug has been well tolerated in an ongoing Phase II study (GA39925) to evaluate the efficacy, safety, and pharmacokinetics of UTTR1147A at 30 µg/kg Q4W, 60 µg/kg Q4W, or 90 µg/kg IV Q4W compared with vedolizumab or placebo in patients with moderate to severe UC. Based on preliminary blinded data, with a data cutoff of 6 March 2020, the overall skin adverse event rate is low at 8.2% (8/98 patients).

Guidelines for management of patients who develop dermatologic reactions are provided in Section 5.1.3.3.

5.1.2.2 Potential Risks

5.1.2.2.1 Administration Site Reactions and Infusion Related Reactions

As with introduction of any foreign biological molecule, the potential risks of UTTR1147A include systemic IRRs and local injection/administration site reactions. IRRs may include true acute allergic/hypersensitivity (e.g., anaphylaxis) reactions and acute pseudoallergic/hypersensitivity-like (e.g., anaphylactoid) reactions. Anaphylaxis and anaphylactoid reactions are the more severe forms of allergic and pseudoallergic reactions, respectively and may have similar or overlapping clinical symptoms. Anaphylaxis is associated with prior exposure to the drug, leading to sensitization and the development of IgE antibodies, and needs to be distinguished from anaphylactoid reactions as the correct diagnosis impacts the decision to re-dose the patient (e.g., patients with anaphylaxis should not be re-challenged). Refer to the UTTR1147A Investigator's Brochure for details about reports of adverse events of infusion related reactions. As UTTR1147A is not administered subcutaneously in this protocol, the potential risk for administration site reactions is not relevant.

5.1.2.2.2 Development of Cross Reacting Anti-Drug Antibodies and Increased Risk for Opportunistic Bacterial and Fungal Infections

Though not seen in human studies to date, there is a possibility that UTTR1147A may induce antibodies that neutralize endogenous IL-22 and, thus, be associated with an increased risk for opportunistic bacterial and fungal infections. Since IL-22 plays a role

MSTT1041A/UTTR1147A—Genentech, Inc.
61/Protocol GA42469, Version 4

in maintaining the integrity of epithelia by promoting its healing and regeneration, neutralizing IL-22 can impact the innate immunity of epithelial tissues (Wolk et al. 2004; Eidenschenk et al. 2014). Mice deficient in IL-22 are more susceptible to certain bacterial and fungal infections when inoculated with a bacterial or fungal challenge (Zheng et al. 2008; De Luca et al. 2010). Similar risks for increased incidence of opportunistic infections are seen with human inborn errors resulting in multiple deficiencies that include IL-22 (Liu et al. 2011; van de Veerdonk et al. 2011; Eidenschenk et al. 2014; Lehman 2014) and in syndromes associated with autoantibodies against multiple cytokines that include IL-22 (Puel et al. 2010).

Refer to the UTTR1147A Investigator's Brochure for details about immunogenicity rates and associated adverse events.

5.1.2.2.3 Enhanced Growth of Existing Epithelial Tumors

There exists a theoretical potential risk for UTTR1147A to promote epithelial tumor progression, likely due to the ability of IL-22 to activate STAT3 in epithelial cells. The cytokine has been known to induce epithelial hyperplasia (Sa et al. 2007; Kirchberger et al. 2013) in vitro and in human tumor cell lines as well as in vivo (Lim and Savan 2014; Bi et al. 2016).

Refer to the UTTR1147A Investigator's Brochure for nonclinical and clinical information regarding neoplasia or epithelial tumors.

5.1.2.3 Laboratory Abnormalities Associated with UTTR1147A (IL-22Fc)

CRP and fibrinogen are acute-phase reactants made in response to hepatocyte stimulation. On-target dose-dependent elevations of CRP and mild elevations of fibrinogen were observed following UTTR1147A administration in nonclinical studies and in clinical studies in healthy volunteers (Studies GA29468 [REDACTED]

[REDACTED] The information collected to date does not indicate that UTTR1147A-mediated CRP and fibrinogen elevations are associated with a safety risk.

Refer to the UTTR1147A Investigator's Brochure for detailed information on laboratory abnormalities.

5.1.2.3.1 C-Reactive Protein Elevation

[REDACTED] CRP elevations have not been associated with signs or symptoms of inflammation, including changes in vital signs such as fever, laboratory values including leukocytosis, or inflammatory cytokines (Rothenberg et al. 2019).

5.1.2.3.2 Fibrinogen Elevation

In healthy volunteers receiving a single dose of UTTR1147A (Study GA29468), mildly increased levels of fibrinogen peaked on approximately Day 8 and returned to near baseline level by Day 29 across all dose levels tested (60 to 120 µg/kg). Overall, increased levels of fibrinogen were less than 2-fold higher than baseline values and were within the normal range of the assay.

Reversible increases in fibrinogen were not deemed clinically significant, and were likely due to direct stimulation of fibrinogen production by hepatocytes. Fibrinogen elevations have not been associated with blood clotting abnormalities or adverse events.

5.1.3 Management of Patients Who Experience Adverse Events

5.1.3.1 Dose Modifications

Dose modifications are not permitted in this study.

5.1.3.2 Treatment Interruption

Treatment interruptions are not applicable in this study, as there are only two doses (see Section 4.6.1).

5.1.3.3 Management Guidelines

Guidelines for management of specific adverse events are outlined in [Table 3](#).

Additional guidelines are provided in the subsections below.

Table 3 Guidelines for Management of Patients Who Experience Adverse Events

Event	Action to Be Taken
Dermatologic reactions ^a	
Grade 1 or 2	
Report details on the dermatologic reactions eCRFAdminister treatment for symptomatic relief, including topical emollients
Grade 3 or 4	
Report as an AESI.Report details on the dermatologic reactions eCRFAdminister treatment for symptomatic relief, including topical emollients, topical corticosteroids, and/or oral antihistamines.If an event is Grade 3, and patient experiences severe discomfort and limitation of self-care activities, consider discontinuing study treatment.If an event is Grade 4, discontinue study treatment.

ADA=anti-drug antibody; AESI=adverse event of special interest; IRR=infusion-related reaction; ULN=upper limit of normal.

^a Refer to Section [5.1.2.1.1](#) for description of *dermatologic reactions*.

Table 3 Guidelines for Management of Patients Who Experience Adverse Events (cont.)

Event	Action to Be Taken
Infusion-related reactions	
General	
 If infusion is stopped, the approximate volume administered should be recorded, as well as all start and stop times.
Grade 1	
 Continue infusion. Reduce infusion rate to 50% of original infusion rate.
Grade 2	
 Interrupt infusion. Administer supportive treatment if indicated per local or institutional standard operating procedures. Upon symptom resolution, resume infusion at 50% of original infusion rate. If infusion reaction reoccurs, discontinue study treatment.
Grade 3 or 4	
 Stop infusion immediately and administer supportive treatment per local or institutional standard operating procedures (see Appendix 3 for guidance on anaphylaxis). Discontinue study treatment. Consider obtaining additional supportive data, if available, to inform the diagnosis of allergic versus pseudoallergic reaction (e.g., serum histamine, serial tryptase measurements).
Cardiac toxicity	
High-sensitivity troponin I or T in the "intermediate" or "indeterminate" range, or $>\text{ULN}$ to $<5 \times \text{ULN}$ (and above baseline)	
 An echocardiogram to assess for cardiac function is recommended. If echocardiogram shows reduced ejection fraction or new hypokinesis or there is clinical evidence of myocarditis and/or pericarditis, discontinue study treatment and report as an AESI. Report as an AESI if it meets criteria for major adverse cardiovascular event.^a
High-sensitivity troponin I or T at a level indicative of myocardial ischemia, $\geq 5 \times \text{ULN}$, or category above "intermediate" or "indeterminate"	
 Discontinue study treatment. An echocardiogram to assess for cardiac function is recommended. Report as an AESI if it meets criteria for major adverse cardiovascular event.^a
Conventional cardiac troponin I or T $>\text{ULN}$, if high-sensitivity immunoassay is not available locally	
 Discontinue study treatment. An echocardiogram to assess for cardiac function is recommended. Report as an AESI if it meets criteria for major adverse cardiovascular event.^a
Major adverse cardiovascular event ^b	
 Discontinue study treatment. Report as an AESI.

ADA=anti-drug antibody; AESI=adverse event of special interest; IRR=infusion-related reaction; ULN=upper limit of normal.

^b Refer to Section [5.2.3](#) for examples of events that qualify as major adverse cardiovascular events.

MSTT1041A/UTTR1147A—Genentech, Inc.
64/Protocol GA42469, Version 4

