severe COVID-19 pneumonia (Lippi and Plebani 2020). In addition, cardiac enzymes will be monitored closely while patients are hospitalized, and cardiovascular complications will be subject to expedited reporting requirements.

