5.2.3 Adverse Events of Special Interest (Immediately Reportable to the Sponsor)

Adverse events of special interest are required to be reported by the investigator to the Sponsor immediately (i.e., no more than 24 hours after learning of the event; see Section 5.4.2 for reporting instructions). Adverse events of special interest for this study are as follows:

- Cases of potential drug-induced liver injury that include an elevated ALT or AST in combination with either an elevated bilirubin or clinical jaundice, as defined by Hy's Law (see Section 5.3.5.8)
- Suspected transmission of an infectious agent by the study drug, as defined below

Any organism, virus, or infectious particle (e.g., prion protein transmitting transmissible spongiform encephalopathy), pathogenic or non-pathogenic, is considered an infectious agent. A transmission of an infectious agent may be suspected from clinical symptoms or laboratory findings that indicate an infection in a patient exposed to a medicinal product. This term applies only when a contamination of the study drug is suspected.
- Suspected infusion related reactions or hypersensitivity reactions, including anaphylaxis, within 24 hours of infusion
- MACE, including:
 - Death due to primary cardiovascular causes (cardiac arrest secondary to progression of disease is excluded)

- Non-fatal myocardial infarction or acute coronary syndrome
- New or worsening heart failure (new globally decreased left ventricular ejection fraction on transthoracic ECHO)
- Grade ≥ 3 dermatologic reactions (as described in Section 5.1.3.3)

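### Myocarditis, pericarditis and new hypokinesis have an explicit AESI rule in only one of Table 3's three troponin rows, so their AESI status can turn on troponin level and local assay

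*Protocol*

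**What the plan says.** Table 3 in Section 5.1.3.3 of the protocol has three troponin rows under cardiac toxicity.

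- **Row 1** covers high-sensitivity troponin in the intermediate or indeterminate range, or above ULN but below 5 x ULN (and above baseline). If ejection fraction has fallen or hypokinesis is new on echocardiogram, or "there is clinical evidence of myocarditis and/or pericarditis, discontinue study treatment and report as an AESI". A separate bullet makes MACE an AESI as well.
- **Row 2** begins "High-sensitivity troponin I or T at a level indicative of myocardial ischemia" and also takes in values of 5 x ULN or more and any category above intermediate.
- **Row 3** covers conventional troponin above ULN, "if high-sensitivity immunoassay is not available locally".

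In rows 2 and 3 study treatment stops, an echocardiogram is recommended, and the only AESI instruction is "Report as an AESI if it meets criteria for major adverse cardiovascular event".

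Section 5.2.3 lists the AESIs for the study. Its MACE entry names cardiovascular death, non-fatal myocardial infarction or acute coronary syndrome, and "New or worsening heart failure (new globally decreased left ventricular ejection fraction on transthoracic ECHO"). A footnote to Table 3 points to that section "for examples of events that qualify as major adverse cardiovascular events". Section 1.4.1 says of MSTT1041A that "cardiovascular complications will be subject to expedited reporting requirements".

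**The concern.** Row 1 sets two AESI triggers: the cardiac finding itself, and MACE. Rows 2 and 3 keep only the second. The same diagnosis can then be an AESI by instruction at one troponin level and an AESI only by judgment at another. It can also differ between a site with a high-sensitivity assay and a site without one, and the protocol permits both. No reason is given for the difference.

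Exacerbation of cardiovascular disease is a named potential risk of MSTT1041A (Section 5.1.1.2.4), and Section 1.4.1 offers expedited reporting as one of the mitigations. AESIs must reach the sponsor within 24 hours (Section 5.2.3), are among the data the DMC reviews (Section 3.1.2), and are summarized by treatment group (Section 6.5). At stake is whether that count means the same thing for every patient.

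**Working it through.** No figure in the protocol bears on this point, so the check is a comparison of text. The inputs are the three troponin rows of Table 3, the AESI and MACE entries in Section 5.2.3, and the stopping list in Section 4.6.1. Each finding is followed through each row.

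| Finding | Row 1: hs-troponin intermediate, or >ULN to <5 x ULN | Row 2: hs-troponin >=5 x ULN, ischemic level, or above intermediate | Row 3: conventional troponin >ULN |
|---|---|---|---|
| Clinical myocarditis or pericarditis, without infarction, acute coronary syndrome, heart failure or cardiovascular death | AESI, stated outright | AESI only if judged to be MACE; not among the examples | As row 2 |
| New regional hypokinesis, global ejection fraction preserved | AESI, stated outright | AESI only if judged to be MACE; not among the examples | As row 2 |
| Globally reduced ejection fraction | AESI, stated outright | Largely covered by the heart-failure item of MACE | As row 2 |
| Infarction, acute coronary syndrome or cardiovascular death | AESI through MACE | AESI through MACE | AESI through MACE |

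Four things follow.

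1. The gap lies in the first two lines of the table. Ejection fraction is largely covered and infarction fully covered in every row.
2. As an illustration, myocarditis at 4 x ULN on a high-sensitivity assay falls in row 1 and is an AESI by instruction. The same diagnosis at 6 x ULN falls in row 2, and on a conventional assay in row 3. In either of those it carries no instruction unless someone calls it MACE.
3. Row 1 lists the cardiac finding and MACE in separate bullets. That suggests the author did not regard the first as already contained in the second, which makes it harder to read the MACE bullet in rows 2 and 3 as silently covering myocarditis.
4. Even within row 1 the two sections disagree: Table 3 calls these findings AESIs, while the AESI list in Section 5.2.3 names none of them and has no other entry that would catch them.

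The treatment rule does not share the gap. Under Section 4.6.1 and Table 3, a patient with any of these findings stops study treatment in all three rows; in rows 2 and 3 the troponin result alone is enough. Only the reporting status differs.

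**The case against.** Several stronger readings are tempting, and the protocol does not support them.

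**That such cases are definitely not AESIs in rows 2 and 3.** The MACE list is open: Section 5.2.3 introduces it as inclusive, and the Table 3 footnote calls the entries examples. An investigator may class a myocarditis as MACE. What stands is that two rows leave this to judgment where one row is explicit.

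**That the worse cases are the ones affected.** This fits the row for 5 x ULN or more. It does not fit the conventional-assay row, which takes any value above ULN; there the fault is dependence on the assay.

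**That the DMC would miss a signal.** Section 3.1.2 gives the DMC access to all available data, including adverse events, serious adverse events, ECGs and laboratory results. A case without the AESI label can still be seen.

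**That expedited reporting fails.** Section 1.4.1 promises expedited reporting, not the AESI label. A case that meets a seriousness criterion, including the investigator's judgment that it is medically significant, reaches the sponsor within the same 24 hours as a serious adverse event. Section 6.5 also tabulates all adverse events, serious adverse events and events leading to treatment discontinuation by arm.

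**That the comparison between arms is biased.** Assignment is randomized and blinded, and the rule is the same in every arm. An undercount is possible; nothing shows that it would differ by arm.

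These points reduce the weight but do not remove the inconsistency. A non-serious case has no automatic 24-hour route in rows 2 and 3, and a serious one may still be absent from the AESI table. In addition, Section 5.3.5.11 keeps events clearly consistent with expected disease progression off the adverse event form, and Section 1.1 names pericarditis among the complications of COVID-19. An explicit AESI instruction would guard against that exclusion. Section 5.3.5.11 does require reporting when there is doubt, so this is a risk and not a certainty.

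**Conclusion.** The point holds as a reporting inconsistency. Followed as written, Table 3 gives myocarditis, pericarditis and new regional hypokinesis an explicit AESI status in one of three troponin rows and leaves it to the investigator in the other two. Section 5.2.3 does not settle the matter. The AESI tabulation by arm and the AESI data sent to the DMC may therefore undercount these events, by an amount that depends on troponin level and on each site's assay.

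The size cannot be computed: the protocol states no expected rate for these events and no mix of assays across sites. The conclusion assumes that at least some investigators read the MACE examples narrowly; if all of them classed such cases as MACE, the AESI count would be complete. Neither the primary analysis nor the stopping of treatment is affected. It is worth correcting because the outcome is tabulated, goes to the DMC and concerns a named risk of MSTT1041A.

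**What to change.** Reconcile Table 3 with Section 5.2.3 so that the same cardiac finding (myocarditis, pericarditis, new hypokinesis or reduced ejection fraction) has the same AESI reporting status in all three troponin rows, and appears with that status in the Section 5.2.3 list. Leave the treatment rules as they are. In the same edit, check the footnote letters: the MACE bullets in the troponin rows carry the letter of the dermatologic footnote, while the MACE footnote has the next letter.

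The cost is wording in two places at the next amendment and a few more expedited reports. No new assessments are needed.
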